**8.1.2 Cohorts 1-9 Investigational Product**

[figure not shown]

[figure not shown]
**Table 8-1. Cohorts 1-9 Investigational Product: AMG 404**

[figure not shown]
A large solid black rectangular area covering the entire content of the table, indicating that the data has been redacted.

[figure not shown]

[figure not shown]

### **8.1.7 Medical Devices**

**There are no investigational medical devices being used in this study.**

Investigational product must be administered using infusion pumps approved for use by the appropriate regulatory authorities for the country in which the subject is undergoing treatment in the outpatient setting. Investigational product solution for infusion will be prepared in bags for IV infusion and delivered through infusion lines that are both compatible with the investigational product. Other non-investigational medical devices may be used in the conduct of this study as part of standard care. Non-investigational medical devices (eg, syringes, sterile needles), that are commercially available are not usually provided or reimbursed by Amgen (except, for example, if required by local regulation). The investigator will be responsible for obtaining supplies of these devices.

**8.1.9 Other Treatment Procedures**

There are no other treatment procedures in this study.

**8.1.10 Product Complaints**

A product complaint is any written, electronic or oral communication that alleges deficiencies related to the identity, quality, durability, reliability, safety, effectiveness, or performance of a drug, combination product, or device after it is released for distribution to market or clinic by either (1) Amgen or (2) distributors or partners for whom Amgen manufactures the material. This includes all components distributed with the drug, such as packaging drug containers, delivery systems, labeling, and inserts.

This includes any investigational/non-investigational product(s) provisioned and/or repackaged/modified by Amgen. AMG 404 [REDACTED] are the investigational products in this study.

Any product complaint(s) associated with an investigational product(s) or non-investigational product(s), supplied by Amgen are to be reported.

Amgen Rave EDC system is being used to report product complaints.

Regardless of the reporting method, all product complaints must be reported to Amgen within 24 hours of discovery.

#### **8.1.11 Excluded Treatments, Medical Devices, and/or Procedures During Study Period**

Any anti-tumor therapy other than the investigational product and protocol-specified therapies, including cytotoxic and/or cytostatic drugs, hormonal therapy, systemic corticosteroids (except for subjects who were receiving  $\leq 10$  mg prednisone or equivalent at the time of enrollment are permitted to remain on it), immunotherapy or any biological response modifiers, any other investigational agent, and other immunosuppressive therapies are excluded.

Primary prophylactic use of hematopoietic growth factors such as granulocyte-colony stimulating factor (G-CSF) is not allowed during the DLT-evaluation period.

Administration of systemic corticosteroids (AMG 404 must be discontinued if  $\geq 10$  mg per day prednisone or equivalent is continued for more than 12 weeks), immunomodulators, and hormonal replacement therapy for the management of toxicities (eg, immune-related adverse events) is allowed. Corticosteroids with no or minimal systemic effect (eg, topical, inhalation) are allowed ( [REDACTED] [REDACTED] [REDACTED] ).

Any live vaccine therapies for the prevention of infectious disease are excluded.

Radiotherapy is not permitted except for palliation of symptoms and should be discussed with the sponsor's Medical Monitor first. Investigators should ensure that the need for radiation does not indicate progressive disease and that for subjects with measurable disease, radiation is not to the sole site of measurable disease.

The following procedures should also not be undertaken within the timeframes specified prior to enrollment and during the study:

- Participation in an investigational study (drug or device) within 21 days of study day 1
- Major surgery within 28 days of study day 1
- Enrollment into another investigational drug or device study

## 8.2 Method of Treatment Assignment

Subjects who meet the eligibility criteria will be assigned to treatment with AMG 404. The treatment assignment date is to be documented in the subject's medical record and on the enrollment CRF.

## 8.3 Blinding

This is an open-label study; blinding procedures are not applicable.

## 8.4 Dose Modification

### 8.4.1 Dose-cohort Study Escalation/De-escalation and Stopping Rules

Planned DLRLMs will be held to review data, monitor safety, and recommend dose changes or other necessary actions, on a per cohort basis. Considering each cohort independently, a DLRLM will occur after the required DLT-evaluable subjects have completed the DLT window:

- All in Cohorts 1 and 2
- The first 6-9 subjects of Cohort 4
- [REDACTED]
- Ad hoc if deemed necessary by the Medical Monitor

The review team will be composed of the investigators, Amgen Medical Monitor, Amgen Global Safety Officer or designated safety scientist, Amgen Early Clinical Development Manager, and Biostatistics representative. Additional members may be added as needed (eg, Clinical Pharmacologist). The Medical Monitor must be in attendance and cannot be represented by a voting designee or delegate. Voting designees can be identified as appropriate by the GSO or site investigators.

The China/Taiwan/Hong Kong specific DLRT will be composed of the investigators in China/Taiwan/Hong Kong or designee, Amgen Medical Monitor, Amgen Global Safety Officer or designated safety scientist, Amgen Early Clinical Development Manager, and Biostatistics representative. Additional members may be added as needed (eg, Clinical Pharmacologist).

A quorum, defined as the majority (defined as greater than or equal to 50%) of actively screening and enrolling investigators or their qualified designee (ie, sub-investigator), Amgen Medical Monitor, and the Amgen Global Safety Officer or delegate must be in attendance for DLRLM to proceed. The DLRLM will be rescheduled if a quorum is not reached.

Voting members of the DLRM will include the Amgen Medical Monitor, the Amgen Global Safety Officer or designated safety scientist, and all actively screening and enrolling investigators or their qualified sub-investigator designee. For cohorts with dosing decisions, the team may recommend escalation to the next planned dose, escalation to an intermediate dose (a dose lower than the next planned dose), continuation or delay in dosing, repetition or expansion of a cohort, de-escalation to a lower dose, or termination of the study. Intra-subject dose escalation is allowed, where applicable. When the subject completes the DLT period the subject may proceed to 480 mg for the following treatment cycle once Cohort 2 has been deemed safe by the DLRT; subjects receiving 480 mg (Cohorts 1-3) who complete the DLT period may proceed to the RP2D once determined if a dose higher than 480 mg is selected as the RP2D. Subjects enrolled at the safety lead-in dose in Cohort 5 may escalate to the RP2D once deemed safe by the China/Taiwan/Hong Kong specific DLRT. All intra-subject dose escalations may occur after consultation with the sponsor as described in Section 6.1. The Amgen Medical Monitor and Global Safety Officer or designee and the majority (defined as greater than or equal to 50%) of actively screening and enrolling investigators participating in the DLRM must cast a positive vote indicating an acceptable safety profile was observed for AMG 404 to allow the dose level modification and/or cohort continuation/expansion to proceed. All available study data including demographics, medical history, concomitant medications, AEs, electrocardiograms (ECGs), vital signs, laboratory results, and emerging PK or pharmacodynamics data will be reviewed. Data to be reviewed may be unqueried.

The dosing schedule is described by a schema in the protocol synopsis.

#### **8.4.2 DLT Definition**

The DLT window (ie, DLT-evaluable period) will be the first 28 days of AMG 404 treatment (starting cycle 1, day 1) for Cohorts 1-9. [REDACTED]

[REDACTED]

[REDACTED] The DLT window may also be extended to assess events starting within the window in case the DLT definition is time dependent.

The subject will be DLT evaluable if the subject has completed the DLT window as described above, or experienced a DLT any time during the DLT window, or has received at least 90% of the planned dose of investigational product(s) and is followed

for at least 1 cycle. A subject will not be DLT evaluable if he/she drops out before completion of the DLT-evaluable period for reasons other than a DLT. All available safety data for subjects who are not DLT-evaluable will still be evaluated and considered in DLRT recommendations (see also Section 13.3).

See Section 6.2.1 for description of replacement of subjects.

An adverse event will be considered related to study treatment (possibly, probably, or definitely related to the study treatment) if there is a suspected “reasonable causal relationship” to the study treatment (ICH E2A), and not only a lack of an alternative explanation for the toxicity. All toxicities will be graded using the CTCAE version 5.0. The occurrence of any of the following toxicities during the DLT evaluation period will be considered a DLT, unless the toxicity is clearly and incontrovertibly due to disease progression or other extraneous causes:

- Any treatment related grade 5 toxicity
- Grade 4 neutropenia or thrombocytopenia > 7 days in duration
- Febrile neutropenia
- Grade 4 anemia
- Grade 3 or 4 non-hematologic toxicity, with the following exceptions:
  - DLT Exemption: Grade 3 endocrinopathies if manageable with replacement therapy
  - DLT Exemption: Grade 3 nausea/vomiting or diarrhea < 72 hours in the absence of maximal medical therapy
  - DLT Exemption: Grade 3 fatigue < 1 week
  - DLT Exemption: Asymptomatic  $\geq$  grade 3 electrolyte abnormalities that last < 72 hours, is not clinically complicated, and resolved spontaneously or responds to conventional medical interventions
  - DLT Exemption:  $\geq$  Grade 3 amylase or lipase that is not associated with symptoms or clinical manifestations of pancreatitis
  - DLT Exemption: Other select lab abnormalities that do not appear to be clinically relevant or harmful to the patient and/or can be corrected with replacement or modifications (eg, grade 3 lymphopenia, grade 3 hypoalbuminemia)
- Recurrent grade 2 pneumonitis
- Delay in cycle 2 treatment for > 14 days due to an adverse event in the dose escalation portion of the study due to study drug-related toxicity
- Any other toxicity requiring permanent discontinuation of AMG 404 or [REDACTED] per Table 13-2 and section 8.4.3.2

Cumulative adverse events profile will be taken into consideration when making decisions on dose escalation or de-escalation.

Any subject meeting the criteria for Hy's Law case (ie, severe drug-induced liver injury) will be considered a DLT. A Hy's Law case is defined as: AST or ALT values of  $\geq 3 \times$  ULN AND with serum total bilirubin level (TBL) of  $> 2 \times$  ULN without signs of cholestasis and with no other clear alternative reason to explain the observed liver-related laboratory abnormalities (see [Table 13-2](#) on hepatotoxicity management and [Section 13.8](#) for further explanation of Hy's law case and Management of Hepatic Function).

If a subject experiences a DLT during the DLT evaluation period, study treatment should be discontinued for that subject. Additionally, any treatment related toxicity meeting the DLT definition after day 28 should result in discontinuation of therapy, unless [Table 13-2](#) recommends otherwise. In subjects with PR, CR or evidence of clinical benefit (as determined by the investigator), an option to continue at the same or at a reduced dose level can be considered once the toxicity returns to the subject's baseline value or CTCAE grade  $\leq 1$  if deemed appropriate by the investigator and sponsor.

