##### **8.4.3.1 Amgen Investigational Product: AMG 404**

Each subject will stay on the dose level assigned unless treatment needs to be stopped. The reason for dose withholds and dose delays is to be recorded on each subject's CRF. AMG 404 may be temporarily withheld or discontinued as necessary, but a partial dose reduction is not permitted.

[REDACTED]

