#### 8.4.3.5 Infusion-related Reactions

Infusion-related reactions may occur with the administration of AMG 404. Monitor patients for signs and symptoms of infusion-related reactions, including pyrexia, chills, rigors, flushing, urticaria, hypotension, dyspnea, wheezing, headache, back pain, and abdominal pain. If an infusion-related reaction is suspected, perform a physical examination, monitor vital signs, monitor pulse oximetry, and perform an ECG if the patient is experiencing chest pain or sustained tachycardia.

For mild or moderate infusion-related reactions, interrupt or slow the rate of infusion. For severe or life-threatening infusion-related reactions, permanently discontinue AMG 404, [REDACTED]. Treatment guidelines for infusion reactions associated with the administration of AMG 404 are provided in [Table 13-4](#). [REDACTED]

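### Protocol 8.4.2's option to continue AMG 404 after a recovered DLT-type toxicity literally reaches events that Table 13-2 lists for permanent discontinuation, with no visible rule of precedence, and its reduced-dose wording contradicts 8.4.3.1

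*Protocol*

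**What the plan says.** **Option.** Protocol 8.4.2 (DLT Definition) sets two defaults. A DLT inside the 28-day window should end study treatment. After the window, "any treatment related toxicity meeting the DLT definition after day 28 should result in discontinuation of therapy", unless Table 13-2 recommends otherwise. The next sentence relaxes this for subjects with PR, CR or investigator-judged clinical benefit: "an option to continue at the same or at a reduced dose level can be considered once the toxicity returns" to baseline or to grade 1 or lower, "if deemed appropriate by the investigator and sponsor".

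**Event-specific rules.**
- Table 13-2 (Appendix 4) assigns each immune-related reaction, by grade, to continuing, withholding or permanently discontinuing AMG 404. Its general considerations describe resumption only for drug that was withheld.
- For infusion reactions, 8.4.3.5 says: "For severe or life-threatening infusion-related reactions, permanently discontinue AMG 404". Table 13-5 rules out any later dose after grade 3 or 4.
- Appendix 8 bars rechallenge for subjects who clearly meet the permanent-discontinuation criteria of Table 13-6.

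**Dose level.** Section 8.4.3.1 says: "Each subject will stay on the dose level assigned unless treatment needs to be stopped". It adds: "AMG 404 may be temporarily withheld or discontinued as necessary, but a partial dose reduction is not permitted".

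**The concern.** A site treating a responder who has recovered from, say, grade 3 pneumonitis finds two instructions. Table 13-2 says AMG 404 is finished for that subject. Section 8.4.2 says continuing can be considered if the investigator and sponsor agree. If they use the option, they comply with one section and breach the other. If they choose a lower dose, they also depart from 8.4.3.1.

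What is at stake is the safety of individual subjects and consistent handling across sites. Colitis and pneumonitis are identified risks in Table 4-1, and events of both have already led to discontinuation of AMG 404, although their grades are not given. Amendment 6 winds down trial activities but allows subjects with continued benefit up to 24 further months of treatment, so the clause can still apply to those remaining on drug.

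**Working it through.** The only arithmetic is a count; the rest is a comparison of texts.

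**1. What the option covers.** It follows the defaults for every DLT in the window and every later toxicity meeting the DLT definition. That definition includes grade 3 or 4 non-hematologic toxicity, with listed exemptions, and closes with any other toxicity requiring permanent discontinuation "per Table 13-2 and section 8.4.3.2". Events that must end treatment are therefore within its literal reach. Its conditions are benefit, recovery and investigator and sponsor agreement. No toxicity is excluded.

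**2. How much of Table 13-2 this touches.**

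| Reaction groups | Number |
|---|---|
| With a permanent-discontinuation entry: pneumonitis, colitis, hepatitis (grade 3-4 only without a clear alternative cause), nephritis, skin, encephalitis, myocarditis, other major-organ reactions at grade 4, recurrent or persistent reactions | 9 |
| Withhold only: hypophysitis, adrenal insufficiency, hypothyroidism, hyperthyroidism, diabetes | 5 |
| Total | 9 + 5 = 14 |

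None of the 9 has an exception for benefit.

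**3. Whether visible text settles precedence for these events.** Section 8.4.2 points to Table 13-2 three times.
- In the last DLT bullet, the pointer helps define a DLT.
- In the post-day-28 sentence, it relaxes the default to stop and does not narrow the option.
- In the Hy's Law paragraph, it concerns liver cases.

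Table 13-2's resumption text covers withheld drug only. That suggests permanently discontinued subjects do not restart, but 8.4.2 does not tie its option to that text. Section 8.4.3.4 refers readers to Table 13-2 without mentioning the option. No visible sentence ranks the two.

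**4. Infusion reactions and liver events.** Grade 3-4 infusion reactions are non-hematologic DLTs by grade, but Table 13-5 expressly excludes further dosing. A Hy's Law case is a DLT under 8.4.2 and largely coincides with the Table 13-6 permanent criteria, after which Appendix 8 forbids rechallenge. For liver cases, 8.4.2 also points to Section 13.8. In both settings the answer is in the protocol; what 8.4.2 lacks is a statement that it yields.

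**5. Dose level.** For AMG 404, 8.4.2 permits a lower level, whereas 8.4.3.1 offers the assigned level or stopping and prohibits a partial reduction. If a move from the 480 mg RP2D to 240 mg, the only lower planned level, is not counted as partial, the first 8.4.3.1 sentence still excludes it.

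**6. Pointer.** Section 8.4.3.5 says "Treatment guidelines for infusion reactions associated with the administration of AMG 404 are provided in" Table 13-4. The list of tables gives that number to chemotherapy nonhematological toxicity; infusion reactions are in Table 13-5.

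**The case against.** **Specific rules govern, and the option is permissive.** A discretionary sentence in a section on DLT definition would ordinarily not displace a mandatory entry in an event-specific table. It can be read as relaxing only 8.4.2's own default, and a site can comply with everything by never using it. This is probably how a careful site would act, and it keeps the point minor. It does not close the gap, because the DLT list in the same section expressly brings in permanent-discontinuation events.

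**Redaction.** Text in 8.4.3 is blacked out and 8.4.3.2 is not visible. A precedence rule could sit there and cannot be counted as missing. This stands in full.

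**Reduced dose may serve other agents.** The option sentence does not name AMG 404. Section 8.4.2 covers a redacted second agent, the SAP refers to up to 13 cohorts, and the list of tables includes chemotherapy dose-modification tables. This also stands, so the conflict is confined to AMG 404.

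**The assigned-level rule is not absolute.** Sections 6.1 and 8.4.1 allow escalation within a subject. True, but those provisions concern upward moves, and 8.4.3.1 separately prohibits partial reduction.

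**A stronger reading to avoid.** A reader might infer that the protocol leaves re-dosing open after a grade 4 infusion reaction or severe drug-induced liver injury. It does not: Table 13-5 and Appendix 8 are express bars, and the wrong table number in 8.4.3.5 is clerical.

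**Conclusion.** The point holds as a minor wording correction in two parts. First, for the 9 of 14 Table 13-2 groups with a permanent-discontinuation entry, the option reaches the event and no visible sentence says which rule governs; for Table 13-5 and Table 13-6 events the bar exists and 8.4.2 only fails to defer to it. Second, for AMG 404 the reduced-dose wording contradicts 8.4.3.1.

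The number of subjects affected cannot be computed and is probably small. Benefit, recovery and agreement are all required, and no DLTs were reported at the 8 October 2019 cut-off (Section 6.4.2). Scans are every 8 (±1) weeks, so PR or CR will not normally be documented inside the 28-day window; the option matters mainly later, or through investigator-judged benefit.

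A reader might infer that the trial's safety results are compromised. The documents do not support that: a DLT is counted whether or not the subject is later re-treated, and no DLT count, mTPI decision, stopping boundary or planned analysis changes. The conclusion assumes that the redacted 8.4.3 text holds no precedence rule.

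**What to change.** 1. Add directly after the option in 8.4.2: *This option does not apply to events for which Table 13-2, Table 13-5 or Table 13-6 requires permanent discontinuation; those rules take precedence.* This is unnecessary if the redacted 8.4.3 text already says so.
2. State in the option sentence that AMG 404 may be continued at the same dose level only, in line with 8.4.3.1. Leave any reduction rules for redacted combination agents as they are.
3. As a clerical correction, change the table number in 8.4.3.5 from 13-4 to 13-5.

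These change dosing rules, so they belong in a protocol amendment with IRB/IEC submission and, where necessary, approval as described in Appendix 3. A memo to sites alone is not enough, and that process is the main administrative cost. The clinical cost is that a few benefiting subjects lose discretionary re-treatment or a reduced AMG 404 dose. The option remains where Table 13-2 only withholds, such as grade 3 colitis or grade 3 rash, and for hematologic DLTs. The SAP needs no change.

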#### **8.4.3 Dosage Adjustments, Delays, Rules for Withholding or Restarting, Permanent Discontinuation**

[figure not shown]
The causality of each adverse event will be assessed individually for each protocol-mandated therapy. [REDACTED]

[REDACTED]

##### **8.4.3.1 Amgen Investigational Product: AMG 404**

Each subject will stay on the dose level assigned unless treatment needs to be stopped. The reason for dose withholds and dose delays is to be recorded on each subject's CRF. AMG 404 may be temporarily withheld or discontinued as necessary, but a partial dose reduction is not permitted.

[REDACTED]

#### 8.4.3.4 Immune-related Adverse Reactions

Adverse events following the administration of AMG 404 may represent an immunologic etiology. Based on clinical experience with other anti-PD-L1 therapies, these immune-related toxicities may occur shortly after the first dose to several months after the last dose of treatment and may affect more than one body system simultaneously. Early recognition and management are critical to reduce complications.

Most immune-related adverse events require adequate evaluation to confirm etiology or exclude other causes. Additional procedures or tests, such as bronchoscopy, endoscopy, or skin biopsy, may be included as part of the evaluation.

Based on the type and severity of the immune-related adverse event, withholding or permanent discontinuation of AMG 404, [REDACTED] may be required, in addition to treatment with corticosteroids and/or other therapies. Dose modification and toxicity management guidelines for immune-related adverse reactions are provided in [Table 13-2](#).

